6.6 Laboratory Safety Tests and Pharmacokinetics Evaluations

An accredited laboratory will function as the central laboratory for all plasma and urine specimens.

Laboratory safety tests will be performed as follows. The laboratory safety tests include:

- Hematology: Complete blood count (CBC) with differential: Screening (V1), Week 1 (V 3), Week 4 (V4), 12 weeks (V6) and 24 weeks (V7) post dosing with study drug.
- Platelet count, PT, PTT, sedimentation rate (sed. rate), CRP only at Visits 1, 3 and 7 only.
- Chemistry: Blood Urea Nitrogen (BUN), creatinine, electrolytes (Na⁺, K⁺, Mg⁺⁺, Ca⁺⁺, CO₂, Cl), albumin, alkaline phosphatase, ALT, AST, LDH, GGT, total bilirubin, total protein, glucose at Screening (V1), Week 1 (V3) , Week 4 (V4), 12 weeks (V7) and 24 weeks (V7) post dosing with study drug.
- Urinalysis: Microscopic RBC and WBC, protein, glucose, nitrites, and specific gravity at Screening (V1), Week 1 (V 3), Week 4 (V4), 12 weeks (V6) and 24 weeks (V7) post dosing with study drug.
- Endocrine: Total testosterone, random cortisol, TSH, T4 (V1, V3, and V7 only);
- At screening visit only, participants must have a hemoglobin A1c
- At V2 –V7, plasma specimens will be collected to assay for the presence of *hSlo* DNA by PCR. These will be kept frozen at -20° C or less at the site for eventual assay

by Sponsor. At Visit 2 specimens should be collected both pre-dosing (to serve as a baseline) and 2 hours post-dosing

6.7 Pharmacokinetics

Blood specimens will be obtained at Visit 2 (predose) and Visits V3-7 for analysis of *hSlo* cDNA with PCR.

Instructions for collection of blood for DNA testing:

Blood

- Collect specimen in heparinized tube
- Centrifuge for 10 minutes at 3000 rpm
- Pipette plasma, freeze immediately and store in labeled plastic vial at -20 (or colder)

7.0 Schedule of Evaluations

The schedule of evaluations is summarized in [Appendix B](#) and described in detail below.

7.1 Visit 1 (Study Week (-) 2 - Screening)

The following evaluations and tests will be performed:

- Preliminary Screening:
 - Obtain written informed consent process for study participant ;
 - Medical history including history of erectile dysfunction to assess eligibility for study treatment;
 - Physical examination including physical examination of penis;
 - Vital signs (BP, heart rate, oral temperature, weight and height)
 - Participant completes the IIEF (screening)
 - Complete screening if entry criteria are met on preliminary screening;
 - Obtain urine for routine urine analysis: microscopic RBC and WBC, protein, glucose, nitrites and specific gravity;
 - Electrocardiogram;
 - Fasting blood specimens for the following laboratory determinations:
 - Hematology: Complete Blood Count (CBC) with differential, platelet count, Partial Thromboplastin (PTT), Prothrombin Time (PT), sedimentation rate (sed rate), C-reactive protein (CRP).
 - Chemistry: Blood Urea Nitrogen (BUN), creatinine, electrolytes (Na⁺, K⁺, Mg⁺⁺, Ca⁺⁺, CO₂, Cl), albumin, alkaline phosphatase, ALT, AST, LDH, GGT, total bilirubin, total protein, glucose;
 - Hemoglobin A1c (diabetic participants);

- Endocrine: total testosterone, random cortisol, TSH, T4
- Schedule next study visit when screening laboratory results are available.

7.2 Visit 2 (Study Week 0 - Administration of study drug)

Based on the participant fulfilling all eligibility criteria following the screening procedures (Visit 1), the participant will be considered eligible to receive study drug. If a participant is unable to receive test material because a clinically significant condition has evolved which, in the investigator's opinion, represents a potential safety risk the patient will be considered a screen failure.

The following tests and evaluations will be performed on eligible participants:

- Adverse events since screening visit;
- Physical examination including examination of the penis for changes since the screening visit;
- Vital signs (BP, heart rate);
- ECG prior to administration of study drug and at 1 and 2 hours post study drug;
- Participant completes SEP and IIEF Urine analysis: microscopic RBC and WBC, protein, glucose, nitrites and specific gravity;
- Plasma specimens will be collected to assay for the presence of *hSlo* DNA by PCR. These will be kept frozen at -20° C or less at the site for eventual assay by Sponsor. Samples will be collected pre-dosing and at 2 hours post dosing.
- Administer study drug. The participant will be observed in the clinic for two hours after the injection. During that time blood pressure and heart rate will be measured and recorded by the nurse every 15 minutes. ECG will be done at one and two hours after administration of study drug and reviewed by a physician at those times. The penis will be inspected for ecchymosis or persistent erection. The participant will be asked if there is any persistent pain at the injection site and will be treated symptomatically, if needed. The participant will be asked if symptoms of malaise, vertigo, light-headedness, and nausea are present. Emergency equipment for resuscitation will be immediately available in the event of an unexpected serious reaction to the study drug.

7.3 Visit 3 (Study Week 1)

The following tests and evaluations will be performed:

- Adverse events and concomitant medications since the last visit;
- Physical examination including examination of penis;
- Vital signs (BP, heart rate);
- Electrocardiogram;
- Obtain plasma for the following laboratory determinations:
 - Hematology: Complete Blood Count (CBC) with differential, platelet count, Partial Thromboplastin (PTT), Prothrombin time (PT), sedimentation rate, C-reactive protein;
 - Chemistry: Blood Urea Nitrogen (BUN), creatinine, electrolytes (Na⁺, K⁺, Mg⁺⁺, Ca⁺⁺, CO₂, Cl), albumin, alkaline phosphatase, LDH, GGT, ALT, AST, total bilirubin, total protein, glucose;
 - Endocrine: total testosterone, random cortisol, TSH, T4;

- Urine analysis: microscopic RBC and WBC, protein, glucose, nitrites and specific gravity;
- Plasma specimens will be collected to assay for the presence of *hSlo* DNA by PCR. These will be kept frozen at -20°C or less at the site for eventual assay by Sponsor.
- Participant completes the IIEF and SEP.
- Schedule next study visit.

7.4 Visit 4 (Study Week 4)

The following tests and evaluations will be performed:

- Adverse events and concomitant medications since last study visit;
- Physical examination including examination of penis
- Vital signs (BP, heart rate);
- Electrocardiogram;
- Obtain plasma for the following laboratory determinations:
- Hematology: Complete Blood Count (CBC) with differential, platelet count;
- Chemistry: Blood Urea Nitrogen (BUN), creatinine, electrolytes (Na⁺, K⁺, Mg⁺⁺, Ca⁺⁺, CO₂, Cl), albumin, alkaline phosphatase, , LDH, GGT, ALT, AST, total bilirubin, total protein, glucose;
- Urine analysis: microscopic RBC and WBC, protein, glucose, nitrites and specific gravity;
- Blood specimens will be collected to assay for the presence of *hSlo* DNA by PCR. These will be kept frozen at -20°C or less at the site for eventual assay by Sponsor.
- Participant completes the IIEF and SEP;
- Schedule next study visit.

7.5 Visit 5 (Study Week 8)

The following tests and evaluations will be performed:

- Adverse events and concomitant medications since last study visit;
- Physical examination including examination of penis;
- Vital signs (BP, heart rate);
- Plasma specimens will be collected to assay for the presence of *hSlo* DNA by PCR. These will be kept frozen at -20°C or less at the site for eventual assay by Sponsor.
- Electrocardiogram;
- Participant completes the IIEF and SEP;
- Schedule next study visit.

7.6 Visit 6 (Study Week 12)

The following tests and evaluations will be performed:

- Adverse events and concomitant medications since last study visit;
- Physical examination including examination of penis;
- Vital signs (BP, heart rate);
- Electrocardiogram;
- Obtain plasma for the following laboratory determinations:
- Hematology: Complete Blood Count (CBC) with differential, platelet count,
- Chemistry: Blood Urea Nitrogen (BUN), creatinine, electrolytes (Na^+ , K^+ , Mg^{++} , Ca^{++} , CO_2 , Cl), albumin, alkaline phosphatase, LDH, GGT, ALT, AST, total bilirubin, total protein, glucose;
- Urine analysis: microscopic RBC and WBC, protein, glucose, nitrites and specific gravity;
- Plasma specimens will be collected to assay for the presence of *hSlo* DNA by PCR. These will be kept frozen at -20°C or less at the site for eventual assay by Sponsor.
- Participant completes the IIEF and SEP;
- Schedule next study visit.

7.7 Visit 7 (Study Week 24) or Exit Visit:

The following tests and evaluations will be performed:

- Adverse events and concomitant medications since last study visit;
- Physical examination including examination of penis;
- Vital signs (BP, heart rate, oral temperature, weight);
- Electrocardiogram;
- Obtain plasma for the following laboratory determinations:
- Hematology: Complete Blood Count (CBC) with differential, platelet count, Partial Thromboplastin (PTT), Prothrombin time (PT), sedimentation rate, C-reactive protein;
- Chemistry: Blood Urea Nitrogen (BUN), creatinine, electrolytes (Na^+ , K^+ , Mg^{++} , Ca^{++} , CO_2 , Cl), albumin, alkaline phosphatase, ALT, AST, LDH, GGT, total bilirubin, total protein, glucose;
- Endocrine: total testosterone, random cortisol, TSH, T4;
- Urine analysis: microscopic RBC and WBC, protein, glucose, nitrites and specific gravity;
- Plasma specimens will be collected to assay for the presence of *hSlo* DNA by PCR. These will be kept frozen at -20°C or less at the site for eventual assay by Sponsor.

- Participant completes the IIEF and SEP.

7.8 Long-term follow-up

All participants upon completion or exit from the study will be presented with written instructions on how to contact the sponsor if they experience any serious adverse event that they consider possibly related to study treatment or study participation. All participants receiving an injection of *h*Maxi-K will continue to be followed after the completion of all study related procedures (Visit 7 or last study visit) for an additional 18 months. These subjects will be contacted by the site at 6 month intervals to evaluate for any safety concerns.

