11.1 Informed Consent	30
12.0 Regulatory Standards.....	30
12.1 Electronic case report forms	30
12.2 Clinical and Regulatory Monitoring.....	30
12.2.1 Study Conduct (Site)	30
12.2.2 Adherence to Reporting Requirements	31
12.3 Participant Confidentiality	31
12.4 Records.....	32
13.0 References	32
Appendix A. Grading of Averse Events	36
Appendix B. Schedule of Events.....	38
Appendix C. Sexual Encounter Profile (SEP).....	39
Appendix D. International Index Erectile Function.....	40

List of Figures

Figure 1: Regulation of Myocyte Tone.....	8
Figure 2. Interaction of Maxi-K channel and nitric oxide. See text for explanation.....	10

List of Tables

Table 1. - Final Dose – h Maxi-K	16
Table 2. Statistical Power	29

Protocol Synopsis

Title	A Double-blind, Placebo-controlled, Parallel Design, Randomized Phase 2A Trial Evaluating the Potential Activity and Safety of hMaxi-K Gene Transfer in Males with Erectile Dysfunction
Study Number	ION 04-ED
Clinical Study Phase	Phase 2A
Number of Centers	One site
Study Objectives	To evaluate the safety and efficacy of a single intracavernous injection of hMaxi K (8000 µg and 16000 µg) or placebo upon penile rigidity or erection in males with erectile dysfunction longer than six months that is attributable to an underlying, stable medical condition.
Study Design	This study is a double-blind, placebo controlled, parallel design, Phase 2A study evaluating the potential activity and safety of a single administration of hMaxi-K (8000 or 16000 µg) or placebo (PBS sucrose 20%) injected into the corpus cavernosum of the penis in men who have been unable to tolerate, do not wish to continue, or have had unsuccessful results with, prior therapy for ED.
Study Participant Population	The study population is men with erectile dysfunction attributable to an underlying, stable medical condition but who are otherwise in good health. The target population is men with erectile dysfunction and those who have been unable to tolerate, do not wish to continue, or have had unsuccessful results with, prior therapy for ED and with an erectile function domain score of IIEF >10 and < 21 at screening and baseline.

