Study Procedures	Following screening and study drug administration at week 0, eligible participants will be evaluated at weeks 1, 4, 8, 12, and 24. At each study visit, participants will have a physical examination including examination of the penis (all visits), vital signs, electrocardiogram (ECG) (all visits). Laboratory evaluations including chemistry and hematology will be done at V1, 3, 4, 6, and 7. Urinalysis will be done V1, 2 (prior to dosing), 3, 4, 6, and 7. Endocrine parameters and PTT, PT, sed rate and CRP will be evaluated at Visit 1, 3 and 7. The participant will complete the erectile function domain of the IIEF and Sexual Encounter Profile (SEP) at screening/baseline and at V2, (SEP and IIEF at V2 prior to dosing) V3, V4, V5, V6, and V7. In all participants, plasma specimens will be collected to assay for the presence of hSlo DNA by PCR (V2-V7). These will be kept frozen at -20°C or less at the site for eventual assay by Sponsor.
Primary Study Outcomes	The primary outcome measures will include the Erectile Function (EF) domain of the International Index of Erectile Function (IIEF), Sexual Encounter Profile (SEP), Questions 2 and 3 from SEP. The IIEF EF domain has a 30-point total score, where higher scores reflect better erectile function. SEP is a diary in which participants record each sexual attempt made throughout the study. The two questions from the Sexual Encounter Profile (SEP) deal with the ability to achieve vaginal penetration (SEP2), and the ability to maintain an erection long enough for successful intercourse (SEP3). The erectile function domain category of the IIEF will be used to evaluate the change in erectile status from baseline following

**Secondary
Study
Outcome****Study Duration****Study Start****Sample Size****Statistical
Analysis**

administration of *h*Maxi-K. Change from baseline on the six questions of the IIEF's Erectile function domain category at every visit after administration of study drug will be calculated and compared among the two dose and one placebo groups.

Safety will be assessed by analysis of adverse experiences, and abnormal findings on clinical laboratory tests, electrocardiogram, and physical examinations.

6 months per participant (approximately 1 year to enroll all participants)

TBD

35 participants; N=11 on 8000 µg; N= 11 on 16000 µg; N= 13 on placebo

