3.0 Study Design

This study is double-blind, placebo controlled parallel design Phase 2A trial evaluating the potential activity and safety of two different doses of *h*Maxi-K (16000 µg, and 8000 µg) given in a single administration relative to placebo injected into the corpus cavernosum of the penis.

The proposed study period is approximately 6 months following the single injection of study drug

per participant. This study will enroll 11 participants at *h*Maxi-K doses of 8000 µg, 11 participants at *h*Maxi-K doses of 16000 µg and 13 on placebo. A maximum of 35 participants will be enrolled.

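### Section 7.8 has the site follow only hMaxi-K men for 18 months, which is not reconciled with the double blind and leaves late safety without a comparably collected placebo rate

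*Protocol*

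**What the plan says.** The Protocol Synopsis describes the trial as blinded on both sides ("This study is a double-blind, placebo controlled, parallel design, Phase 2A study") and run at one site; Section 3.0 repeats the blinding. The synopsis gives the duration as "6 months per participant (approximately 1 year to enroll all participants"). Each man's last blinded assessment is at Week 24, the visit headed "7.7 Visit 7 (Study Week 24) or Exit Visit".

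Section 7.8 then sets out two tiers of later safety follow-up:

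- **Everyone, passively.** "All participants upon completion or exit from the study will be presented with written instructions on how to contact the sponsor" about a serious event that the man himself thinks may be related.
- **Active men only, by contact.** "All participants receiving an injection of *h*Maxi-K will continue to be followed" after Visit 7 or the last study visit, "for an additional 18 months". On who does this and how often: "These subjects will be contacted by the site at 6 month intervals to evaluate for any safety concerns".

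Protocol Section 10.3 says the final SAP will precede the breaking of the code, but it does not link release of allocation to the last man's Visit 7. The SAP plans no analysis of the 18-month phase. Protocol Section 8.0 refers the reader to a Section 7.9 for post-study follow-up, whereas the text is in 7.8.

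**The concern.** Being on the contact list means having received hMaxi-K. If a site that is still treating and assessing men works from that list, it learns which finished men were active and, by elimination, which were on placebo. With about a year of accrual at one site, that can happen while later men are still attending visits or waiting to be dosed.

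Two things are at stake:

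- **The blind for men still in the study.** Staff who can match allocation to outcome and injection experience in finished men may form expectations, or guess the arm of a man in front of them. Protocol Section 9.3 makes causality the principal investigator's best estimate, so that judgement is the most exposed.
- **Interpretation of late events.** The primary objective in Protocol Section 2.0 is safety compared with placebo. The population has conditions such as hypertension, atherosclerosis, diabetes and previous stroke, so some events over 18 months are to be expected whatever the treatment. Active collection in the hMaxi-K arms only gives no concurrent rate gathered in the same way.

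**Working it through.** The plan gives no figure for this overlap, so there is none to reproduce. The check is a calendar calculation.

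**Inputs from the protocol**

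- 35 men: 11 + 11 = 22 active and 13 placebo (Section 3.0).
- Accrual of about 1 year (synopsis), taken as 52 weeks.
- Last blinded visit at Week 24 after dosing (Section 7.7).
- Contacts every 6 months for 18 months after Visit 7 (Section 7.8): 18 / 6 = 3 per man.

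**Assumptions.** Dosing is evenly spaced over an accrual period of A weeks, so man i (i = 0 to 34) is dosed at week A × i / 34. Six months is taken as 26 weeks. Nobody leaves early; an early exit would bring that man's first contact forward.

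**Step 1: dates.** First contact falls 24 + 26 = 50 weeks after dosing. The last Visit 7 falls at week A + 24. A man reaches first contact before the last Visit 7 if

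A × i / 34 + 50 < A + 24, that is, A × i / 34 < A − 26.

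**Step 2: counts.** Expected active men are the count × 22 / 35.

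| Accrual A (weeks) | Condition on i | Men reaching first contact before last Visit 7 | Expected active |
|---|---|---|---|
| 26 or less | none | 0 | 0 |
| 39 | i < 11.3 | 12 | 7.5 |
| 52 | i < 17 | 17 | 10.7 |
| 65 | i < 20.4 | 21 | 13.2 |

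**Step 3: who is still in the study.** With A = 52, the first contact is due at week 50 and the last Visit 7 is at week 52 + 24 = 76. At week 50, the men with Visit 7 still ahead are those with 52 × i / 34 + 24 > 50, so i = 18 to 34, which is 17 men. Two of these (i = 33 and 34) are not yet dosed.

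**Step 4: earlier identification.** If the site has to know at each man's own Visit 7 whether to enter him in long-term follow-up, disclosure starts at week 24 and reaches up to 34 of the 35 men before the last man's Visit 7. The protocol does not say which applies.

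**Step 5: late safety.** Active contact covers 22 hMaxi-K men and no placebo men. If no event of a given type is seen, the one-sided 95% upper limit is 1 − 0.05^(1/22) = 12.7%. Following the 13 placebo men as well would allow a 22 v 13 comparison, but a weak one. One-sided Fisher exact power at 0.05, for assumed event rates, is about 15% for 20% v 5%, 42% for 30% v 5% and 70% for 40% v 5%.

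**The case against.** The strongest reply is that nothing in either document says the site is told anyone's allocation during the trial. Section 10.3 reads more like one code break than release man by man, and a site that was still blinded could simply call every finisher, which Section 7.8 does not forbid. That stands: a reader might infer that the blind is broken before the last Week 24 visit, and the documents do not support so firm a statement. What they support is that 7.8, carried out as written and on time, needs knowledge that the blind withholds, and that no rule resolves this.

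Other parts of the reply also stand:

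- A reader might assume that the callers are the people who assess visits. Section 7.8 names only the site.
- A man on the list has completed or left his blinded visits, and the list shows active v placebo, not dose. Randomisation is central and kits are blinded, so knowing one man's arm does not directly disclose another's.
- A reader might infer that IIEF and SEP results are compromised. Those are completed by participants who remain blinded, and the documents show no direct route from a finished man's allocation to another man's answers.
- It would be wrong to say that placebo men yield no late safety data, since they keep the self-report route. What is missing is collection comparable to that in the hMaxi-K arms.
- The follow-up is described as surveillance, and the power figures show that a placebo comparison would have little inferential value.

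The reply does not remove the conflict. Withholding the list would protect the blind, but the protocol does not require it, and doing so without other arrangements would delay the scheduled contacts.

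**Conclusion.** The point holds as an unreconciled conflict between Section 7.8 and the double blind. It is not a finding that unblinding will occur. Under uniform accrual over the protocol's approximate year, about 17 of 35 men, about 11 of them active, fall due for first contact before the last Visit 7. The result depends on accrual: it is 0 at 26 weeks or less and about 21 at 65 weeks. It also assumes that the site works from an active-only list and that allocation is not held back.

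The consequence for men still in the study is indirect, through expectation or guessing, and bears mainly on causality assessment. The missing placebo follow-up is a secondary matter: a comparably collected rate in 13 men would be descriptive context, not a test. Confidence is medium, because the disclosure is inferred from what 7.8 requires and is not stated.

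**What to change.** **Preferred.** Reword Section 7.8 so that all participants who received study drug, hMaxi-K or placebo, are contacted at 6-month intervals, at least until the last Visit 7, database lock and code break. Add to the SAP that late events are listed and summarised descriptively by randomised arm. The contact list then says nothing about allocation.

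**Alternative.** If active follow-up is to stay limited to hMaxi-K men, state that allocation is withheld from site assessors until the last Visit 7, database lock and code break, and that contacts before then are made by personnel who take no part in assessments. This protects the blind but adds no placebo information.

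**Same edit.** Correct the Section 8.0 cross-reference from 7.9 to 7.8.

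**Cost.** The preferred option adds at most 13 × 3 = 39 short contacts to the 22 × 3 = 66 already planned, and fewer if placebo contacts stop at code break. It needs a protocol amendment and probably matching consent wording. The alternative needs an amendment and a separate caller.
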